10.2.3. Storage and Stability of INCB039110

The bottles of tablets should be stored under ambient conditions at 15°C to 30°C (59°F to 86°F).

10.3. Accountability, Handling, and Disposal of Study Drug

Responsibility for drug accountability at the study site rests with the investigator; however, the investigator may assign some of the drug accountability duties to an appropriate pharmacist or other designee. Inventory and accountability records must be maintained and readily available for inspection by the study monitor and are open to inspection at any time by any applicable regulatory authorities.

The investigator or designee will be expected to collect and retain all used, unused, and partially used containers of study drug until the end of the study. The investigator or designee must maintain records that document:

- Delivery of study drug to the study site.
- Inventory of study drug at the site.
- Subject use of the study drug, including pill or unit counts from each supply dispensed.
- Return of study drug to the investigator or designee by subjects.

These records should include dates, quantities, batch or serial numbers (if available), and the unique code numbers (if available) assigned to the investigational product and study subjects.

The investigational product must be used only in accordance with the Protocol. The investigator will also maintain records adequately documenting that the subjects were provided the correct study drug specified.

Completed accountability records will be archived by the site. At the completion of the study, the investigator or designee will oversee shipment of any remaining study drug back to the sponsor or its designee for destruction according to institutional standard operating procedures. If local procedures mandate site destruction of investigational supply, prior written approval must be obtained from Incyte.

11. STUDY ADMINISTRATION

11.1. Data Management

11.1.1. Data Collection

The investigator will be provided with a CRF for each subject. Entries made in the CRF must be verifiable against source documents; any discrepancies should be explained and documented. The investigator will be responsible for reviewing all data and CRF entries and will sign and date the designated pages in each subject's CRF, verifying that the information is true and correct. The investigator is responsible for the review and approval of all responses.

11.1.2. Data Management

Data management will be performed from CRFs. All CRF data will be entered into a validated database. All data entry, verification, and validation will be performed in accordance with the current standard operating procedures of the Data Management Department at the sponsor or its designee. The database will be authorized for lock once all defined procedures are completed.

11.2. Study Monitoring

Qualified representatives of the sponsor or its designee, "study monitors," will monitor the study according to a predetermined monitoring plan. Monitoring visits provide the sponsor with the opportunity to:

- Evaluate the progress of the study.
- Verify the accuracy and completeness of CRFs.
- Assure that all Protocol requirements, applicable laws and/or regulations, and investigator's obligations are being fulfilled.
- Resolve any inconsistencies in the study records.

The investigator must allow the study monitors to periodically review, at mutually convenient times during the study and after the study has been completed, all CRFs and office, hospital, and laboratory records supporting the participation of each subject in the study. The CRFs and other documentation supporting the study must be kept up-to-date by the investigator and the research staff at the investigative site. These study materials must be available for review by the study monitor, and/or other qualified representatives of the sponsor or its designee, at each monitoring visit.

The study monitor will review the various records of the study (CRFs, subject medical and laboratory records, and other pertinent data). The study monitor will verify the CRF data against original source documentation for accuracy and completeness. The study monitor will identify data discrepancies and collaborate with the investigator and research staff to resolve the discrepancies in a timely manner. Protocol deviations will also be identified and recorded on a "Protocol Deviation Log." The study monitor will follow an "Issue Escalation" plan in order to ensure that each issue identified during a monitoring visit is appropriately documented, reported, and resolved in a timely manner in accordance with the plan's requirements.

11.3. Protocol Adherence

The principal investigator must obtain IRB or IEC approval for the investigation. Initial IRB or IEC approval and all materials approved by the IRB or IEC for this study including the subject ICF and recruitment materials must be maintained by the investigator and made available for inspection.

Each investigator must adhere to the Protocol as described in this document and agree that changes to the Protocol, with the exception of medical emergencies, must be discussed and approved, firstly, by the sponsor or its designee and, secondly, by the IRB or IEC. Each investigator is responsible for enrolling subjects who have met the Protocol inclusion and exclusion criteria. The IRB or IEC that granted original approval, or the IRB or IEC currently responsible for overseeing the conduct of the study, must be notified of all changes in and deviations from the Protocol that may increase risk to the subject, and/or that may adversely affect the rights of the subject or validity of the investigation. The investigator must send a copy of the approval letter from the IRB or IEC to the sponsor or its designee and retain the original in the site study regulatory file.

Major eligibility deviations must be reported to the IRB or IEC in accordance with the IRB or IEC requirements. During the course of the study, the monitor must notify the sponsor or its designee of subjects found not to have met eligibility criteria. The medical monitor, in collaboration with the investigator, will determine if the subject should be withdrawn from the study.

11.4. Financial Disclosure

All clinical investigators participating in clinical studies subject to FDA Regulation Title 21 Code of Federal Regulations (CFR) Part 54 – Financial Disclosure by clinical investigators, are required before study initiation to submit a completed clinical investigator Financial Disclosure Request Form that sufficiently details any financial interests and arrangements that apply. For the purpose of this regulation, clinical investigator is defined as any investigator or subinvestigator who is directly involved in the treatment or evaluation of research subjects, including the spouse and each dependent child of the clinical investigator. These requirements apply to both US and foreign clinical investigators conducting covered clinical studies.

Any new investigators or subinvestigators added to the covered clinical study during its conduct must also submit a completed clinical investigator Financial Disclosure Request Form. During a covered clinical study, any changes to the financial information previously reported by a clinical investigator must be reported to the sponsor or its designee. At the conclusion of the covered clinical study, the clinical investigators will be reminded of their obligation to report to the sponsor or its designee any changes to the financial information previously reported. The clinical investigators will also be reminded that they must report any changes in their financial information for a period of 1 year after completion of the covered clinical study.

12. QUALITY CONTROL AND QUALITY ASSURANCE

12.1. Sponsor Audits

At some point during the study, individuals from the sponsor's Quality Assurance department and/or their authorized representative may visit the investigator's site to conduct an audit of the study. The purpose of this visit will be to determine the investigator's adherence to the Protocol, applicable regulations, and the sponsor's procedures, in addition to assessing the accuracy of the study data. Before initiating this audit, the investigator will be contacted by the sponsor to arrange a convenient time for this visit. The investigator and staff are expected to cooperate with the auditors and allow access to all subject records supporting the CRFs and other study-related documents.

12.2. Inspection by Regulatory Authorities

At some point during the investigational product's development program, a regulatory authority may visit the investigator to conduct an inspection of the study and the site. The investigator and staff are expected to cooperate with the inspectors and allow access to all source documents supporting the CRFs and other study-related documents. The investigator must immediately notify the sponsor when contacted by any regulatory authority for purposes of conducting an inspection.

13. ETHICS

13.1. Ethical Conduct of the Study

This study will be performed in accordance with ethical principles that have their origin in the Declaration of Helsinki and conducted in adherence to the study Protocol, GCPs as defined in Title 21 of the US CFR Parts 50, 54 56, 312, and Part 11, as well as ICH GCP consolidated guidelines (E6) and applicable regulatory requirements.

13.2. Written Informed Consent

Informed consent documentation that includes both information about the study and the ICF will be prepared and given to the subject. This document will contain all elements required by the ICH E6 Guideline for GCP and any additional elements required by local regulations. The document must be in a language understandable to the subject and must specify who informed the subject. Where required by local law, the person who informs the subject must be a physician.

The principal investigator at each center will ensure that the subject is given full and adequate verbal and written information about the nature, purpose, and the possible risk and benefit of the study. Subjects must also be notified that they are free to discontinue study drug and withdraw from the study at any time. The subject should be given the opportunity to ask questions and allowed time to consider the information provided.

The subject's signed and dated ICF must be obtained before conducting any study procedures. The principal investigator must maintain the original, signed ICF. A copy of the signed ICF must be given to the subject. The investigator should inform the subject's primary physician about the subject's participation in the study if the subject has a primary physician and if the subject agrees to the primary physician being informed.

Preparation of the ICF is the responsibility of the investigator and must include all elements required by the ICH GCP, and applicable regulatory requirements, and must adhere to the ethical principles that have their origin in the Declaration of Helsinki. A template will be provided by the sponsor or its designee. The sponsor or its designee must review and approve all changes to site-specific ICFs. The ICF must include a statement that the sponsor or its designee and regulatory authorities have direct access to subject records. Before the beginning of the study, the IRB or IEC must provide the investigator with written approval/favorable opinion of the written ICF and any other information to be provided to the subjects.

13.3. Ethics Review

It is the responsibility of the investigator to assure that all aspects of the ethics review are conducted in accordance with the Declaration of Helsinki as described in the ICH E6: Guideline for GCP, and/or local laws, whichever provides the greatest level of protection for the study participants. The Protocol and any information supplied to the subject to obtain informed consent, including written ICFs, subject recruitment procedures (eg, advertisements), and written information to be provided to subjects (information leaflets), must be reviewed and approved by a qualified IRB/IEC before enrollment of participants in the study. Before initiation of the study,

the sponsor or its designee must receive documentation of the IRB or IEC approval, which specifically identifies the study/protocol, and a list of the committee members.

The principal investigator is responsible for informing the IRB or IEC of any amendment to the Protocol in accordance with local requirements. Protocol amendments and revisions to the ICF must be submitted to and approved by the IRB or IEC.

Investigators must submit progress reports to the IRB or IEC in accordance with the IRB or IEC requirements and local regulations. Annual re-approval of the study must be obtained. Copies of progress reports and annual re-approvals must be sent to the sponsor or its designee.

The principal investigator is also responsible for providing the IRB or IEC with reports of any reportable serious adverse drug reactions from any other study conducted with the investigational product. The sponsor or its designee will provide this information to the principal investigator.

When the sponsor or its designee provides the investigator with a safety report, the investigator must promptly forward a copy to the IRB or IEC.

After completion or termination of the study, the investigator must submit a final report to the IRB or IEC and to the sponsor or its designee.

The investigator, as part of the records retention requirements for the study, must maintain documentation of all submissions, correspondence, and approvals to and from the IRB or IEC.

Each clinical investigator is responsible to conduct the study in accordance with the Protocol, all applicable laws, regulations, and GCP according to ICH guidelines.

13.4. Data Privacy

The investigator and the sponsor or its designee must adhere to applicable data privacy laws and regulations. The investigator and the sponsor (or its designee) are responsible for ensuring that sensitive information is handled in accordance with local requirements (eg, HIPAA).

Appropriate consent and authorizations for use and disclosure and/or transfer (if applicable) of protected information must be obtained.

14. DATA HANDLING AND RECORDKEEPING

14.1. Inspection of Records

The sponsor or its designee will be allowed to conduct site visits to the investigation facilities for the purpose of monitoring any aspect of the study. The investigator agrees to allow the monitor to inspect the drug storage area, study drug stocks, drug accountability records, subject charts and study source documents, and other records relative to study conduct.

The investigator must ensure that all records pertaining to the conduct of the clinical study (as listed above) are adequately maintained for a period of 2 years after the last approval of a marketing application in an ICH region and until there are no pending or contemplated marketing applications in an ICH region, or at least 2 years have elapsed since the formal termination of clinical development of the investigational product.

14.2. Retention of Records

The principal investigator must maintain all documentation relating to the study for a period of 2 years after the last marketing application approval, or if not approved, 2 years following the termination of the test article for investigation. If it becomes necessary for the sponsor or the regulatory authority to review any documentation relating to the study, the investigator must permit access to such records.

The investigator must not destroy any records associated with the study without receiving approval from Incyte. The investigator must notify the sponsor or its designee in the event of accidental loss or destruction of any study records. If the investigator leaves the institution where the study was conducted, the sponsor or its designee must be contacted to arrange alternative record storage options.

Whenever possible, an original recording of an observation must be retained as the source document. However, a photocopy of a record is acceptable, provided it is legible and is a verified copy of the original document.

All CRF data entered by the site (including audit trail), as well as computer hardware and software (for accessing the data), will be maintained or made available at the site in compliance with applicable record retention regulations. The sponsor will retain the original CRF data and audit trail.

14.3. Confidentiality

Subject names will not be supplied to the sponsor or its designee if applicable. Only the subject number and subject's initials will be recorded in the CRF, where permitted; if the subject's name appears on any other document (eg, laboratory report), it must be obliterated on the copy of the document to be supplied to the sponsor or its designee. Study findings stored on a computer will be stored in accordance with local data protection laws. The subjects will be informed that representatives of the sponsor or its designee, IRB or IEC, or regulatory authorities may inspect their medical records to verify the information collected, and that all personal information made available for inspection will be handled in strictest confidence and in accordance with local data protection laws.

15. PUBLICATION POLICY

By signing the study Protocol, the investigator and his or her institution agree that the results of the study may be used by the sponsor, Incyte Corporation (Incyte), for the purposes of national and international registration, publication, and information for medical and pharmaceutical professionals. If necessary, the authorities will be notified of the investigator's name, address, qualifications, and extent of involvement. The terms regarding the publication of study results are contained in the agreement signed with the sponsor or its designee. The signed agreement is retained by the sponsor or its designee.

APPENDIX A. INFORMATION REGARDING EFFECTIVENESS OF CONTRACEPTIVE METHODS

For Subjects Participating in the Study:

The following methods that can achieve a failure rate of less than 1% per year when used consistently and correctly are considered as highly effective birth control methods.

Such methods include:

- Combined (estrogen and progestogen containing) hormonal contraception associated with inhibition of ovulation¹
 - oral
 - intravaginal
 - transdermal
- Progestogen-only hormonal contraception associated with inhibition of ovulation¹
 - oral
 - injectable
 - implantable²
- Intrauterine device (IUD)²
- Intrauterine hormone-releasing system (IUS)²
- Bilateral tubal occlusion²
- Vasectomised partner^{2,3}
- Sexual abstinence⁴

¹ Hormonal contraception may be susceptible to interaction with the IMP, which may reduce the efficacy of the contraception method.

² Contraception methods that in the context of this guidance are considered to have low user dependency.

³ Vasectomised partner is a highly effective method provided of avoiding pregnancy that partner is the sole sexual partner of the WOCBP trial participant and that the vasectomised partner has received medical assessment of the surgical success.

⁴ In the context of this guidance, sexual abstinence is considered a highly effective method only if defined as refraining from heterosexual intercourse during the entire period of risk associated with the study treatments. The reliability of sexual abstinence needs to be evaluated in relation to the duration of the clinical trial and the preferred and usual lifestyle of the subject.

Source: [CTFG 2014](#).

APPENDIX B. PHARMACOKINETIC ANALYTICAL PARAMETERS

C_{ave}	Average steady-state plasma concentration ($AUC_{0-12h}/12h$ or $AUC_{0-24h}/24h$)
C_{max}	Maximum observed plasma concentration
C_{min}	Minimum observed plasma concentration during the dosing interval
T_{max}	Time to maximum plasma concentration
AUC_{0-t}	Area under the single-dose plasma concentration-time curve from Hour 0 to the last quantifiable measurable plasma concentration, calculated by the linear trapezoidal rule for increasing concentrations and the log trapezoidal rule for decreasing concentrations
$AUC_{0-\tau}$ (ie, AUC_{0-12h} or AUC_{0-24h})	Area under the steady-state plasma concentration-time curve over 1 dosing interval (ie, from Hour 0 to 12 for BID administration or from Hour 0 to 24 for QD administration), calculated by the linear trapezoidal rule for increasing concentrations and the log trapezoidal rule for decreasing concentrations
λ_z	Apparent terminal phase disposition rate constant, where λ_z is the magnitude of the slope of the linear regression of the log concentration versus time profile during the terminal phase
$t_{1/2}$	Apparent plasma terminal phase disposition half-life (whenever possible), where $t_{1/2} = (\ln 2) / \lambda_z$
Cl/F	Oral dose clearance
V_z/F	Apparent oral dose volume of distribution
Fluctuation	Steady-state fluctuation ($(C_{max} - C_{min})/C_{ave}$)

In addition, the following PK parameters may be calculated, whenever possible, for each subject based on the urine INCB050465 concentrations:

A_e	Amount of drug excreted in the urine over sampling interval
Cl_r	Renal clearance, where $Cl_r = A_e/AUC$
% Excreted or f_e	percent excreted in the urine, where % Excreted = $100 (A_e/\text{dose})$

Pharmacokinetic calculations will be performed, if appropriate, using commercial software such as WinNonlin® (Pharsight Corporation, Mountain View, CA). Additional details of analyses will be described in the Statistical Analysis Plan.

APPENDIX C. EASTERN COOPERATIVE ONCOLOGY GROUP (ECOG) PERFORMANCE STATUS

Grade	Performance Status
0	Fully active, able to carry on all predisease performance without restriction
1	Restricted in physically strenuous activity but ambulatory and able to carry out work of a light or sedentary nature, eg, light house work, office work
2	Ambulatory and capable of all selfcare but unable to carry out any work activities. Up and about more than 50% of waking hours
3	Capable of only limited selfcare, confined to bed or chair more than 50% of waking hours
4	Completely disabled. Cannot carry on any selfcare. Totally confined to bed or chair
5	Dead

Source: [Oken et al 1982](#).

APPENDIX D. RESPONSE CRITERIA FOR LYMPHOMA

LYMPHOMA RESPONSE CRITERIA – The Lugano Classification ([Cheson et al 2014](#))

Site	PET–Based Response	CT/MRI–Based Response
	Complete metabolic response:	Complete radiologic response (all of the following):
Lymph nodes and extralymphatic sites	Score 1, 2, or 3 with or without a residual mass on 5PS ^a .	Target nodes/nodal masses must regress to ≤ 1.5 cm in LDi.
Nonmeasured lesion	Not applicable.	Absent.
Organ enlargement	Not applicable.	Regress to normal.
New lesions	None.	None.
Bone marrow	No evidence of FDG-avid disease in marrow.	Normal by morphology; if indeterminate, IHC negative.
	Partial metabolic response:	Partial remission (all of the following):
Lymph nodes and extralymphatic sites	
 Score 4 or 5^a with reduced uptake compared with baseline and residual mass(es) of any size. 	
 ≥ 50% decrease in SPD of up to 6 target measurable nodes and extranodal sites. When a lesion is too small to measure on CT, assign 5 mm × 5 mm as the default value. When no longer visible, 0 × 0 mm. 
For a node > 5 mm × 5 mm but smaller than normal, use actual measurement for calculation.

Nonmeasured lesions	Not applicable.	Absent/regressed, but no increase.
Organ enlargement	Not applicable.	Spleen must have regressed by > 50% in length beyond normal.
New lesions	None.	None.
Bone marrow	Residual uptake higher than uptake in normal marrow but reduced compared with baseline (diffuse uptake compatible with reactive changes from chemotherapy allowed). If there are persistent focal changes in the marrow in the context of a nodal response, consideration should be given for further evaluation with MRI or biopsy at interval scan.	Not applicable.

Site	PET–Based Response	CT/MRI–Based Response
	No metabolic response:	Stable disease:
Target nodes/nodal masses, extranodal lesions	Score of 4 or 5 ^a with no significant change in FDG uptake from baseline at interim or EOT.	< 50% decrease from baseline in SPD of up to 6 dominant, measurable nodes and extranodal sites; no criteria for progressive disease are met.
Nonmeasured lesions	Not applicable.	No increase consistent with progression.
Organ enlargement	Not applicable.	No increase consistent with progression.
New lesions	None.	None.
Bone marrow	No change from baseline.	Not applicable.
	Progressive metabolic disease:	Progressive disease (requires at least one of the following):
Individual target nodes/nodal lesions	
Individual target nodes/nodal lesions:
 
 • Score 4 or 5^a with an increase in intensity of uptake from baseline and/or • New FDG-avid foci consistent with lymphoma at interim or EOT assessment. 
Extranodal lesions:
 
 • New FDG-avid foci consistent with lymphoma at interim or end-of-treatment assessment. 
New lesions:
 
 • New FDG-avid foci consistent with lymphoma rather than another etiology (eg, infection, inflammation). If uncertain regarding etiology of new lesions, biopsy or interval scan may be considered. 
Bone marrow:
 
 • New or recurrent FDG-avid foci. 	
PPD progression:
 
 • An individual node/lesion must be abnormal with all of the following: 
 ○ LDi > 1.5 cm ○ Increase by ≥ 50% from PPD nadir ○ An increase in LDi or SDi from nadir 
 ▪ 0.5 cm for lesions ≤ 2 cm ▪ cm for lesions > 2 cm • In the setting of splenomegaly, the splenic length must increase by > 50% of the extent of its prior increase beyond baseline (eg, a 15-cm spleen must increase to > 16 cm). If no prior splenomegaly, must increase by at least 2 cm from baseline. • New or recurrent splenomegaly. • New or clear progression of preexisting nonmeasured lesions. • Regrowth of any previously resolved lesions. • A new node > 1.5 cm in any axis. • A new extranodal site > 1.0 cm in any axis; if < 1.0 cm in any axis, its presence must be unequivocal and must be attributable to lymphoma. • Assessable disease of any size unequivocally attributable to lymphoma. • New or recurrent involvement of the bone marrow.

SPS = 5-point scale; LDi = longest transverse diameter of lesion; MRI = magnetic resonance imaging; PPD = cross product of the LDi and perpendicular diameter; SDi = shortest axis perpendicular to the LDi; SPD = sum of the product of the perpendicular diameters for multiple lesions.

^a PET 5-point scale: 1, no uptake above background; 2, uptake ≤ mediastinum; 3, uptake > mediastinum but ≤ liver; 4, uptake moderately > liver; 5, uptake markedly higher than liver and/or new lesions; X, new areas of uptake unlikely to be related to lymphoma.

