7.5.2. FDG-PET or Combined PET-CT

If positron emission tomography (PET) using [¹⁸F] fluorodeoxyglucose (FDG) or combined PET-CT is used as a functional imaging tool for staging or response assessment of lymphoma as a part of the standard of care (eg, in subjects with HL or DLBCL), the results obtained during any study phase will be captured in the CRF.

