### **7.2.2. Best Overall Response and Overall Response Rate**

[figure not shown]
Best overall response is the best response recorded during the study treatment prior to and including the first PD, in the order of CR, VGPR, PR, MR, SD, PD, and NE. In the case of SD, assessment must meet the SD criteria at least once on or after Day 42. Subjects who fail to meet this criterion will have best response of PD if the next available assessment after the initial assessment indicates PD or will have best response of NE if there are no additional assessments available.

A subject is considered a responder if they have a best overall response of CR or PR (CR, VGPR, PR, or MR for subjects with WM postbaseline).

The ORR is the proportion of responders. Subjects who do not have sufficient baseline or on-study response assessment information to be adequately assessed for response status will be included in the denominators in the calculation of ORR.

Best overall response will be summarized descriptively. The ORR will be estimated with 95% CIs. Confidence intervals will be calculated based on the exact method for binomial distributions.

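### Appendix D's CT/MRI definition of complete response sets no condition for measured extranodal lesions, so persistent extranodal tumour is compatible with a complete response that counts in the ORR

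*Protocol*

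**What the plan says.** Protocol Appendix D writes out the lymphoma response criteria in a PET column and a CT/MRI column. In the CT/MRI column:

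- **Complete response.** The heading, "Complete radiologic response (all of the following", makes the conditions cumulative. In the row for nodes and extralymphatic sites the cell reads "Target nodes/nodal masses must regress to ≤ 1.5 cm in LDi". The other rows deal with lesions that were not measured, enlarged organs, new lesions and marrow.
- **Partial remission.** The same row requires a "≥ 50% decrease in SPD of up to 6 target measurable nodes and extranodal sites".
- **Stable disease.** The size condition is "< 50% decrease from baseline in SPD of up to 6 dominant, measurable nodes and extranodal sites", in a row labelled "Target nodes/nodal masses, extranodal lesions".

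Protocol 9.4.2 takes response from the investigator's assessment and counts CR or PR as an objective response. SAP 7.2.2 does the same: "A subject is considered a responder if they have a best overall response of CR or PR". It adds no extranodal condition. Central imaging review is optional, and only for the Part 3 expansion cohorts (Protocol 7.5, SAP 7.2.1).

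PET is not mandatory. Protocol 7.5.2 captures PET results if PET "is used as a functional imaging tool for staging or response assessment of lymphoma as a part of the standard of care", and Tables 5 and 7 list it on the same footing. Some subjects can therefore be expected to be assessed by CT or MRI alone.

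**The concern.** Extranodal disease is counted when a scan is tested for partial remission or stable disease, but drops out when it is tested for complete response. The nodal wording cannot easily be stretched to include it, because the stable-disease row names nodes and extranodal lesions as separate items. A measured lesion is not one of the nonmeasured lesions that must be absent. The organ-enlargement row may catch some liver or spleen involvement, but not a measured lesion in an organ of normal size.

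At stake are the CR count and the ORR. A subject with persistent measured tumour can satisfy each listed CT line and, if called CR, is a responder. The PET column scores nodes and extralymphatic sites together and has no such gap, so the same disease could be classified differently according to a site's imaging practice. Two sites reading similar CT scans could also differ, one following the appendix and the other the publication it cites.

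**Working it through.** The plan states no figure on this point, so there is none to reproduce. The check applies the Appendix D CT lines, as written, to constructed scans. SPD is the sum of longest × perpendicular diameter over target lesions. In every case the other CR rows (nonmeasured lesions, organs, new lesions, marrow) are assumed to be satisfied.

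**1. Extranodal lesion unchanged.** Node 3 × 2 cm shrinks to 1.5 × 1.0 cm; extranodal target stays at 5 × 4 cm.
- Baseline SPD = 3×2 + 5×4 = 26.0 cm².
- On-study SPD = 1.5×1.0 + 5×4 = 21.5 cm².
- Change = (21.5 − 26.0)/26.0 = −17.3%.
- The nodal CR line holds (longest diameter 1.5 cm). Partial remission fails, since the decrease is below 50%. The stable-disease size line holds.

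**2. Extranodal lesion grown.** Node 2.0 × 1.5 cm to 1.4 × 1.0 cm; extranodal target 4.0 × 3.0 cm to 4.5 × 3.5 cm.
- SPD goes from 3.0 + 12.0 = 15.0 to 1.4 + 15.75 = 17.15 cm², a rise of 14.3%.
- The extranodal product rises by 15.75/12.0 − 1 = 31%, short of the 50% over nadir in the CT progression rule.
- The nodal CR line holds; partial remission fails; the size criterion for progression is not met.

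**3. Nodes only, as a control.** Node 1.8 × 1.5 cm to 1.5 × 1.2 cm.
- SPD goes from 2.7 to 1.8 cm², a decrease of 33.3%.
- CR holds and partial remission fails, although no extranodal disease exists. This happens because CR uses an absolute limit and partial remission a relative one.

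The control locates the defect. Meeting CR without meeting PR is not itself an error. What matters is that cases 1 and 2 meet the CR lines with measured tumour still present. If CR also required that no measured extranodal disease remain, cases 1 and 2 would no longer be CR and case 3 would be unaffected.

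**4. Effect on the ORR.** One subject moves it by 1/n: 1/15 = 6.7 points, 1/30 = 3.3 points. The responder counts below are assumed for illustration; the intervals are exact binomial, as the plan specifies.

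| Cohort | Responders without the subject | With one such subject |
|---|---|---|
| 15 | 5/15 = 33.3% (95% CI 11.8 to 61.6) | 6/15 = 40.0% (16.3 to 67.7) |
| 30 | 10/30 = 33.3% (17.3 to 52.8) | 11/30 = 36.7% (19.9 to 56.1) |

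**The case against.** The strongest reply is that the ORR does not rest on Appendix D alone. Protocol 4.3.2 and 9.4.2 and SAP 2.3.2 and 7.2.1 point to the published criteria, and the SAP response sections do not cite the appendix. An assessor who works from the publication may apply a condition that the appendix lacks. This stands as a limit on the effect. Appendix D is nevertheless the only place in these documents where the lymphoma criteria are written out, and Protocol 5.7.1 sends investigators there for the definition of progression.

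A line may have been lost in extracting the table from the PDF; a number is visibly missing from the CT progression cell. That cannot be excluded. The CR cell does read as a complete sentence, and the multi-line partial-remission cell in the same table survived. Checking the original settles it.

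One CT progression item refers to assessable disease of any size attributable to lymphoma. Taken literally, it would make the unchanged tumour in case 1 progressive disease. But it would do the same to most partial remissions and stable disease, and it follows items about new nodes and new sites, so it is not a workable safeguard for CR.

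A reader might infer that the plan converts stable disease into CR because best overall response ranks CR first. It does not. That ranking works across visits, while the investigator assigns one category at each visit. The scan in case 1 fits both the CR lines and the stable-disease size line, and nothing obliges the investigator to choose CR.

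The planned target-lesion listing and waterfall plot would also make a CR with a 17% decrease visible. That helps detection, but no step in the plan acts on it.

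**Conclusion.** The gap is real as written: in the CT/MRI column, persistent measured extranodal disease is compatible with complete response, and a subject so classified counts in the ORR. Any bias is upward, at 6.7 points per subject in a cohort of 15 and 3.3 in a cohort of 30.

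This rests on the appendix being applied literally and on the table text being complete. It concerns only lymphoma subjects assessed without PET who have a measured extranodal target and meet every other CR line. CLL and Waldenström macroglobulinemia have their own criteria. Protocol 7.5.2 names HL and DLBCL as examples where PET may be standard of care, which narrows the exposed group further.

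The documents do not give the number affected, so they do not support a claim that the reported ORR will be inflated by a particular amount. Having a measured extranodal lesion on CT is exposure to the gap, not misclassification.

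Severity is minor to moderate. The primary endpoint is safety, ORR is a secondary endpoint reported descriptively, and no hypothesis is tested (Protocol 9.3).

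**What to change.** **Protocol.** Check the CT/MRI complete-response cell of Appendix D against its cited source, and add that no measured extranodal (extralymphatic) disease remains.

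**SAP.** In 7.2.2, add a consistency check of each CT-based CR against the target-lesion data already planned for Listing 2.6.3. Query the investigator where a measured extranodal lesion is still recorded. The investigator's assessment stays the basis for the ORR, as Protocol 9.4.2 has it; a CR should not be withheld from the count merely because a query is open.

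**Cost.** One line in the appendix, one programmed check and no new data. A few CRs may become PR or SD once queried.
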